1.6.2 Specific Objectives

1. To understand the perspectives of stakeholders (school teachers, administrators, parents, community leaders and students) on a school-based FA training (YoFA) program among SSC.

Hypothesis 1: The perspectives of stakeholders like school administrators, teachers, parents, community leaders, and school children needs to be understood to design a comprehensive YoFA program

2. To assess school children's Knowledge, Attitudes (willingness to) and Practices (self-efficacy) (KAP) on trauma/injury FA via the built YoFA training to stop LTBs.

Hypothesis 2: School children have limited knowledge, self-efficacy and practices regarding trauma/injury FA

3. To evaluate the effectiveness and usability of the YoFA training program for SSC to respond to LTBs safely and promptly in their environs.

Hypothesis 3: The YoFA training Program is effective in improving the KAP of SSC and it is usable within the school and community setting.

4. To determine the barriers associated with implementing the YoFA program among early SSC in the Fako Division.

Hypothesis 4: There exist some barrier/challenges in implementing a YoFA training

program in secondary schools.

CHAPTER TWO

LITERATURE REVIEW

It is important to understand some aspects regarding first aid training for children in schools. Here, we will be highlighting the relevance of Advanced Trauma Life Support concepts, the injury burden among school children, the qualifications of potential educators, and the appropriateness of school-based training. There is a clear consensus on the necessity and benefits of teaching first aid in schools, as it equips children with essential life skills, enhances their confidence, and promotes a safer environment. Future research should focus on developing effective training programs tailored to this age group, considering the emotional aspects of learning and the varied contexts in which children may need to apply their skills particularly in our setting.

First aid training is an essential aspect of emergency preparedness, particularly for children aged 10 to 14 years. This age group is increasingly exposed to various risks, both in schools and everyday life. Here, we will explore four key areas related to first aid training for children: the concept of Advanced Trauma Life Support (ATLS), the injury burden among school children, potential educators of first aid, and the appropriateness of implementing first aid training in schools.

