3.5 SAMPLE SIZE AND SAMPLING

Sample Size Calculation

For the cross-sectional study and Intervention

Assuming an equal number of control and intervention subjects, a prevalence of the outcome in the controls of 0.5, and a prevalence in the intervention group of 0.75 (an absolute increase of 25%)[17] with a power of 80% and 5% error margin, we calculated the sample size needed using STATA.

Estimated sample sizes for a two-sample proportions test Pearson's chi-squared test using STATA

$H_0: p_2 = p_1$ versus $H_a: p_2 \neq p_1$ Study parameters:

```
alpha = 0.0500
power = 0.8000
delta = 0.2500 (difference)
p1 = 0.5000
p2 = 0.7500
```

Estimated sample sizes:

N =	116
N per group =	58

If we assume a 15% drop out rate, we have a sample size of $15\% * 116 = 17.4$ Thus, sample size is $116 + 17.4 = 133.4 \approx 134$

For each group, the sample needed is therefore **N = 67 students. Sampling**

Since this is a crisis area, we will use convenience sampling to choose the Health Areas (HAs) that are secure and geographically accessible (safest) in both HDs. Out of seven (7) and eight (8) HAs in Buea and Tiko HDs respectively, there are 4 accessible HAs in each. Of these, one HA from each HD does not harbour a state secondary school (SSS).

Leaving us with 3 HAs to work with in each HD. Each of these HAs contains 1 SSS but for 1 HA from each District which has 2 SSSs. We would work with all these State schools to ensure that we get students from most of the communities around the schools, thus ensuring the representativeness of our samples. To avoid spill-over, one of the districts will be selected as intervention HD and the other as the control.

Stratified random sampling will be used to select the students for the study from a sampling frame of the list of students in each classroom concerned.

We would use probability proportionate to size to choose the specific number of students to participate in the study per classroom (A, B, and C) for each class.

[figure not shown]

Figure 5: Selection of HAs and Schools for Implementation.

*GHS-Government High School; BGS-Bilingual Grammar School; GTHS Government Technical High School; GBHS government Bilingual High School

For each school distribution of the participants will be as follows:

A) For the Qualitative part:

The qualitative part will be sampled purposively.

Table 2: Number of Participants to be chosen per school for the FGDs

Health District	Schools	FGD Category of Participant	Number per school

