3.7 STUDY VARIABLES AND TYPE

Variables

Outcome variables

1. Knowledge Change: to determine whether or not there was an overall change in knowledge before and after the training (dichotomous).
2. Test scores: to measure the educational efficacy of the first aid training before and after the intervention in comparison with the control group (continuous)
3. Self-efficacy ratings: Participants' self-perceived efficacy in performing first aid skills or their confidence levels in "Stopping the bleed and/or calling for help" (dichotomous)

4. Response time: The time taken by participants to respond to simulated first-aid scenarios or emergencies that require them to either stop an LTB or call for help or refer (continuous).
5. The number of participants who make use of the skills taught during the 3 months post-training but before the final assessment (Discrete).

Exposure Variables

The exposure variables include training on LTBs from injury first aid and the use of these services by the trained students (e.g., the number of persons assisted or referred during the follow up period of the training).

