3.11 DATA ANALYSIS PLAN

A difference-in-difference analysis would be done to assess the change in KAPs before and after the intervention in. The posttest would be done immediately after the 4 days of training for each pool and 3 months after the training to assess the need for refresher course planning.

The exposure variables include training on LTBs from injury first aid and the use of these services by the trained students (e.g., the number of persons assisted or referred during the follow-up period of the training).

We will analyze survey data using R Software with a combination of descriptive statistics and parametric and non-parametric tests to establish statistically significant differences between pre- and post-test results and between the intervention and control groups.

Table 7: Objectives and their Indicators

Objective	Activities/process	Data collection tools	Data Source	Indicators
1. To understand the perspectives of stakeholders on YoFA training program among SSC	- In-depth interviews	-In-depth interview guides	School teachers, administrators, parents, community leaders and students	
2. To assess school children's KAP (willingness and self-efficacy on trauma/injury FA via the built YoFA training to stop LTBs.	- survey	-Questionnaire	- students	- Obtain baseline KAP Scores
3. To evaluate the effectiveness and usability of the YoFA training program for SSC to respond to LTBs safely and promptly in their environs.	-Training following a specific STB and LFRs program -Training students on specific modules of LTB FA - Pre and post test -Simulation exercises	- Use adapted tools from the SBEAT - Questionnaires - Evaluation form with questions how? What was the situation?where, and how?	Stakeholders, teachers, parents, students	- Change in knowledge scores -At least 50% of stakeholders rate the program as good/ expectations met - 70% of students rate the program as good/expectations met - Number of children who made use of the FA skills taught
4. To determine the barriers associated with implementing the YoFA program among early SSC in the Fako Division.	- Interviews - Survey	-Interview guides - Questionnaires	- Stakeholders, - Teachers, students	- Perceived reasons and challenges that hinder FA training in schools.

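### The sample size is set for one 5% test of an unnamed yes/no outcome, while five unranked outcomes at two post-tests leave nothing to decide whether the training is effective

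*Protocol*

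**What the plan says.** **Sample size (Protocol 3.5).** The calculation assumes "a prevalence of the outcome in the controls of 0.5, and a prevalence in the intervention group of 0.75", "with a power of 80% and 5% error margin", and equal groups. The software output is headed "Estimated sample sizes for a two-sample proportions test Pearson's chi-squared test using STATA", with a two-sided alternative, and gives 58 per group. The outcome is not named.

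**Outcomes (3.7).** Five are listed with no primary: knowledge change (dichotomous), test score (continuous), self-efficacy (dichotomous), response time (continuous), and use of the skills over the 3 months after training (discrete). The second reads "Test scores: to measure the educational efficacy of the first aid training before and after the intervention in comparison with the control group (continuous".

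**Success criteria (3.6, Step 3).** A separate list covers emergency calls made, people helped, bleeds dealt with or referred, intention to act, and scenario performance. All are to be compared between the arms. Most of these are not in the 3.7 list.

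**Analysis (3.11).** A difference-in-difference analysis of change in knowledge, attitudes and practices (KAP) is planned, with post-tests straight after training and at 3 months. The section also plans "parametric and non-parametric tests to establish statistically significant differences between pre- and post-test results and between the intervention and control groups". Table 7 gives a third set of indicators for Objective 3, starting with change in knowledge scores.

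**Hypothesis 3 (1.6.2).** "The YoFA training Program is effective in improving the KAP of SSC and it is usable within the school and community setting". No decision rule is attached.

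**The concern.** A 5% error rate and 80% power are properties of one specified test. Here the test that was sized cannot be identified. Two of the five listed outcomes are dichotomous, and either could be the one meant. The analysis section then spreads significance testing over several outcomes and two occasions without saying which comparison carries the conclusion.

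If that stays open, the outcome and time point that support effectiveness can be settled after the results are known, and the real chance of a false claim exceeds the stated 5%. The results are meant to inform school and health policy (chapter 4), so the claim should rest on a test chosen in advance.

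**Working it through.** **1. Reproduce the protocol's figure.** Inputs from 3.5: p1 = 0.50, p2 = 0.75, two-sided alpha 0.05, power 80%, equal groups. With pooled variance and no continuity correction,

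n = [1.960·√(2·0.625·0.375) + 0.842·√(0.50·0.50 + 0.75·0.25)]² / 0.25²
= [1.960·0.6847 + 0.842·0.6614]² / 0.0625 ≈ 3.605 / 0.0625 ≈ 57.7, so 58 per group.

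This matches. Power at 58 per group is 80.2%. The arithmetic is right for one test.

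**2. Count the tests.** The protocol gives no count, so this is an inference.
- Upper count: outcomes 1 to 4 at two post-tests, plus skill use once: 4 × 2 + 1 = 9.
- Lower count: each outcome once: 5.
- The criteria in 3.6 and the pre/post tests would raise the count. Response time may lower it, because 1.1.2 times it during training sessions.

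**3. Chance of at least one false positive at 0.05 each.** If independent, it is 1 − 0.95^k: 22.6% for k = 5 and 37.0% for k = 9. The other rows come from simulating equally correlated normal test statistics. The correlations are assumptions.

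| Correlation | 5 tests, two-sided | 9 tests, two-sided | 5 tests, favouring training | 9 tests, favouring training |
|---|---|---|---|---|
| 0 | 22.6% | 37.0% | 11.9% | 20.5% |
| 0.3 | 21.0% | 32.6% | 10.6% | 16.5% |
| 0.5 | 18.3% | 26.9% | 9.1% | 13.4% |
| 0.7 | 14.9% | 20.3% | 7.5% | 10.1% |
| 0.9 | 10.1% | 12.4% | 5.0% | 6.2% |

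The benchmark is 5% for the two-sided columns and 2.5% for the favourable direction. Every entry exceeds it.

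**4. Cost of keeping all tests and correcting by Bonferroni (0.50 against 0.75).**
- Five tests (alpha 0.01): power is 58% at 58 per group and 69% at the 70 per group of Table 5. 80% power needs 87 per group.
- Nine tests (alpha 0.0056): power is 50% and 61%. 80% power needs 97 per group.

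**5. What a continuous primary would do to power.** Suppose 50% against 75% reflects a normal score cut at the control median. The shift is then 0.674 SD (not a protocol figure). With 58 per group:
- Post-test scores only: 95%.
- Change from pretest: the effect becomes 0.674/√(2(1 − ρ)), where ρ is the pre/post correlation. Power is 72% at ρ = 0, 86% at 0.3 and 95% at 0.5.
- Post-test adjusted for pretest: the residual SD is multiplied by √(1 − ρ²), for example √(1 − 0.25) = 0.87 at ρ = 0.5, against √(2 × 0.5) = 1 for the change score. This is never worse than the post-test alone.

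The gain therefore depends on the analysis and on ρ, which the protocol does not give.

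**The case against.** The best counter-argument is that the protocol points to an efficacy outcome without labelling it. The test score is the only outcome in 3.7 worded as measuring educational efficacy against the control group. Change in knowledge scores comes first among the Table 7 indicators for Objective 3, and 3.11 opens with a difference-in-difference analysis. Skill use concerns skills that only the trained arm was taught, so it bears more on usability. Section 3.11 ties the 3-month test to planning refresher courses. All of this stands, and it is why the test score is the natural primary. It is still not a designation: 3.5 was computed for a proportion, so it was not sized for that score, and 3.2 also treats the later evaluation as a measure of impact.

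A reader might infer that any one significant result among nine would be enough to declare the programme effective. The protocol does not say so. Hypothesis 3 joins better KAP with usability, and requiring every component is an equally possible reading. That reading would not inflate the error, but the 80% power for one outcome would then not be the power for the claim. Neither rule is written.

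A reader might also take 37% as the actual error. That needs nine independent tests, yet knowledge change and test score overlap and the same pupils are tested repeatedly.

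Nor is sizing on a yes/no outcome a mistake. The 95% power in step 5 belongs to a post-test-only comparison and does not carry over to a change score.

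Finally, a multiplicity procedure may sit in a statistical analysis plan that is not shown. Its absence is not the point made here. Which outcome decides the hypothesis, and which one the sample size serves, belong in the protocol.

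**Conclusion.** The point holds in this form: the protocol names neither the outcome and time point that decide the effectiveness part of Hypothesis 3 nor the outcome for which 3.5 was calculated. The stated 5% is thus tied to no listed outcome, and nothing in the text holds it for the effectiveness claim.

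If a significant result on any one outcome were accepted, the two-sided chance of at least one false positive would be about 10% to 23% for five tests and 12% to 37% for nine. These figures rest on my count of tests and on assumed correlations from 0 to 0.9. The direction does not depend on either, but the exact size does. The figure of 58 per group is correct for a single test of 0.50 against 0.75.

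**What to change.** - **3.7 and 3.11:** name one primary outcome at one time point. The continuous test score compared between arms (outcome 2) is the natural choice: it is already collected and consistent with the planned difference-in-difference analysis. Preferably adjust it for the pretest score.
- **Time point:** the sponsor chooses the immediate or the 3-month test before data are seen. Either can be defended.
- **Decision rule:** state that the effectiveness part of Hypothesis 3 is judged on this comparison at two-sided 5%.
- **Other outcomes and the other time point:** make them secondary, reported with confidence intervals and not used alone to claim effectiveness. Say how the criteria in 3.6 and Table 7 relate to this list.
- **3.5:** restate the sample size for the named outcome, with its SD and the pre/post correlation given as assumptions.

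The cost is protocol wording, with no new instrument or visit. Whether the planned numbers suffice will show when 3.5 is restated. The small downside is that a positive secondary outcome can no longer carry the claim alone. The change corrects multiplicity only. Table 5 has one school per arm, and pupil-level tests cannot guarantee 5% in that design whichever outcome is primary.

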1.1.2 Operational Definitions

First Aid Knowledge: Measured by a standardized questionnaire assessing participants' understanding of basic first aid principles, including recognition of injuries, appropriate responses, and the use of first aid equipment. A pre-test and post-test will be administered to evaluate knowledge gained from the training.

Practical Skills Proficiency: Evaluated through hands-on assessments where participants (children) demonstrate specific first aid techniques, such as identification of injuries including wounds and take action towards care. Proficiency will be rated on a scale from 1 to 5 by the trainers based on accuracy and confidence in performing the skills.

Training Attendance: Defined as the percentage of scheduled training sessions attended by each participant. Attendance will be tracked through a sign-in sheet at each

session, with a minimum attendance threshold set at 80% to qualify for the evaluation phase.

Behavioral Intent to Use First Aid: Assessed using a Likert scale survey administered after the training program, measuring participants' self-reported likelihood of applying first aid skills in real-life situations. This will include scenarios where they might encounter injuries or emergencies.

Community Engagement: Measured by the number of community members who give favourable feedback on the activities of the YoFA trainees during and after the intervention. The effectiveness of these activities will be evaluated through feedback forms from community members.

Self-Efficacy in First Aid: Evaluated using a self-report scale that assesses participants' confidence in their ability to perform first aid tasks taught. This will be measured before and after the training program to determine changes in self-efficacy levels.

Injury Response Time: Measured by timing participants' responses in simulated emergency scenarios during training sessions. The time taken to initiate appropriate first aid measures will be recorded and analyzed to assess improvement over the course of the program.

These will help us ensure that the study effectively measures the impact of the YOFA Training Program on early secondary school children in the Fako Division, providing clear metrics for evaluation and analysis.

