We will consider criteria for success as the proportion of persons who made an emergency call to an adult, teacher, the emergency number of the regional hospital, to a medical professional or to the closest Health Facility to the incident. The proportion of people who received help. The proportion of persons whose bleeds or LTBs were alleviated or attended to or who were referred for better management. Furthermore, the intention to treat/carryout the desired first aid act in the phase of an acute incident requiring FA. Lastly, we would like to evaluate the number of students who perform well during the scenarios to evaluate the need for knowledge revamping/refresher course on the aspects of FA taught. And all these, we shall compare the outcomes between the intervention and control groups.

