1 = Strongly Disagree with the statement made	2 = Disagree with the statement made	3 = Neutral you neither agree nor disagree to the statement made	4 = Agree with the statement made	5 = Strongly agree with the statement made
 1 ☆☆☆☆☆	 2 ★★☆☆☆	 3 ★★★★☆	 4 ★★★★☆	 5 ★★★★★

ITEM	Value per 5-point Likert scale response, n (%)				
	1	2	3	4	5
1. I feel that I can know what to do with the YoFA skills if I see someone in need					
2. I found the skills taught too complicated to use.					
3. I thought the skills were easy to use.					
4. I think that I would need help from the staff to be able to use these skills.					
5. I found the training topics in the YoFA skill set to be strongly related/closely associated to each other.					
6. I thought there were too many changes/ups and downs in the skill set taught					
7. I would imagine that most other children of my age would learn to use these skills very quickly.					
8. I thought the skills were really hard to use.					
9. I felt very confident using the skill set.					
10. I needed to learn a lot of things before I could start applying the skill set					

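### Self-efficacy is defined as a graded before-and-after scale but typed as dichotomous in section 3.7, and the printed pre/post questionnaire contains no such scale

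*Protocol*

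**What the plan says.** Section 1.1.2 (Operational Definitions) describes self-efficacy as "Evaluated using a self-report scale that assesses participants' confidence in their ability to perform first aid tasks taught". It adds: "This will be measured before and after the training program to determine changes in self-efficacy levels". This is a graded measure, taken twice, with change as the target.

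Section 3.7 (Study Variables and Type) lists five outcome variables and gives each a type. Test scores and response time are continuous. Outcome 3, headed as self-efficacy ratings, covers "their confidence levels in 'Stopping the bleed and/or calling for help' (dichotomous". No cut-point is given there or elsewhere, and no reason for having one.

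Section 3.8 prints the tools. The pre/post questionnaire asks in item 10A, yes or no, whether the pupil would help someone who is bleeding. Item 38 is graded, but it asks about excitement for the training. The only graded confidence item is in the adapted usability scale: "9. I felt very confident using the skill set".

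Section 1.6.2, objective 2, equates the practices part of KAP with self-efficacy. Section 3.11 plans a difference-in-difference analysis of the change in KAP.

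**The concern.** Sections 1.1.2 and 3.7 describe one outcome in two incompatible ways. If 3.7 is followed, a pupil who gains several steps without crossing the cut counts as unchanged, and a pupil who gains one step across it counts as a full success. A change in levels, which 1.1.2 asks for, cannot be recovered from that.

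The printed tools add a second problem. If item 10A is the source of the two-category outcome, then what is measured is willingness to help, not confidence on a scale. If usability item 9 is the source, it cannot serve at pre-test or in untrained controls, so no difference-in-difference is possible.

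Self-efficacy is a named component of objective 2 and feeds Hypothesis 3 through the KAP comparison. At stake are the meaning of the outcome, some avoidable loss of power, and a result that depends on where the cut falls.

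**Working it through.** **Inputs from the protocol (section 3.5).** Two-sided alpha 0.05, power 80%, equal groups, and "a prevalence of the outcome in the controls of 0.5, and a prevalence in the intervention group of 0.75". The stated size is 58 per group, 67 after dropout; Table 5 has 70.

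**Inputs not in the protocol, assumed here.** The rating is normal with SD 1 in both arms, the cut is at the control median, pupils are independent, and the section 3.5 proportions apply to self-efficacy. Section 3.5 does not name its outcome.

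**Step 1: reproduce the plan's figure.** With mean proportion 0.625,

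n = [1.960·√(2·0.625·0.375) + 0.842·√(0.25 + 0.1875)]² / 0.25² = 57.7, so 58 per group. This agrees with the protocol.

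**Step 2: power of the two-category outcome, post-test.**

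Φ{[0.25·√n − 1.960·0.6847] / 0.6614}. At n = 58 this is Φ(0.850) = 80.2%.

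**Step 3: power if the rating is kept, post-test.** The equivalent shift is d = Φ⁻¹(0.75) − Φ⁻¹(0.50) = 0.6745. Power is Φ(d·√(n/2) − 1.960). At n = 58 this is Φ(3.632 − 1.960) = 95.3% (95.0% by the exact t-test).

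| n per group | cut at median | full score | points forgone |
|---|---|---|---|
| 58 | 80.2% | 95.3% | 15.0 |
| 67 | 85.7% | 97.4% | 11.7 |
| 70 | 87.2% | 97.9% | 10.7 |

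A single five-point item with even control categories, simulated at the same shift and cut between its categories, forgoes about 7 to 14 points.

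**Step 4: difference-in-difference.** With equal baselines and pre/post correlation r, the full score has power Φ(d / √(4(1−r)/n) − 1.960). At n = 58 this is 87%, 95% and 99.7% for r = 0.3, 0.5 and 0.7. The two-category and five-level versions were simulated at n = 58:

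| r (assumed) | two categories | five levels | points forgone |
|---|---|---|---|
| 0.3 | 57% | 82% | 25 |
| 0.5 | 64% | 91% | 27 |
| 0.7 | 76% | 98% | 22 |

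A second set of category boundaries at r = 0.5 gave 67% against 87%, a gap of 20 points. At 70 per group, r = 0.7 and even categories, the simulation gave 83% against 99%, a gap of about 15. The range for a five-level rating is therefore roughly 15 to 27 points. A truly continuous score widens it a little: 95% against 64% at r = 0.5.

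**Step 5: how far the answer moves with the assumptions (post-test, 58 per group).** With a median cut, the loss is 11.9 points at d = 0.3, 21.1 at d = 0.5 and 1.8 at d = 1.0. With 80% of controls above the cut, it is 18.1 at d = 0.3, 37.8 at d = 0.5 and 37.6 at d = 0.6745. With 90% above the cut at d = 0.6745, it is 57.1.

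**The case against.** The strongest reply is that nothing graded may be lost. The printed questionnaire holds only a yes/no item, so the type in 3.7 may describe that item correctly. Section 3.9 names knowledge, practical skills and helping behaviour as the quantitative variables and does not mention self-efficacy. This has force. It does not remove the conflict, because 1.1.2 still promises a graded scale taken twice. It moves part of the problem to the tools.

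A second reply is that scoring rules and cut-points often belong in a statistical analysis plan, which is not at hand. That is right for the cut-point, so its absence is not a fault in itself. But 3.7 does fix the variable type, and a plan that analysed the full rating would contradict it.

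Four stronger readings are tempting and are not supported:

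- *A definite loss of so many points.* The protocol gives no effect, number of levels, correlation or cut for self-efficacy, so every power figure is conditional.
- *A shortfall against the planned power.* The sample size was computed for a two-category post-test outcome, and at that effect such an outcome keeps its 80%. What is lost is power that could have been had.
- *An analysis already committed to discarding the grading.* Section 3.11 sets no specific analysis for self-efficacy; the loss follows only if 3.7 is applied to a graded rating.
- *The same fault in the scenario criterion.* Section 1.1.2 says "Proficiency will be rated on a scale from 1 to 5 by the trainers", and section 3.6 wants to "evaluate the number of students who perform well during the scenarios". A reader might infer a cut of that rating, but 3.6 does not link the two, and it ties the count to the need for a refresher course.

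**Conclusion.** The point holds as an inconsistency between sections 1.1.2, 3.7 and 3.8, with an avoidable loss of information if 3.7 is applied to a graded rating. Under the assumptions listed, the power forgone is about 11 to 15 points post-test and roughly 15 to 27 points for a difference-in-difference on a five-level rating. It falls to near zero for large effects and exceeds 50 points for an extreme cut.

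All figures treat pupils as independent, as section 3.5 does, although Table 5 has one school per arm. They show the relative cost of the cut, not the trial's real power. Self-efficacy is one of five listed outcomes, and two others are already continuous, so this is worth correcting but does not undermine the study as a whole.

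**What to change.** 1. In section 3.7, retype outcome 3 as ordinal or continuous: the full confidence rating on the scale defined in 1.1.2.
2. Analyse it by difference-in-difference on the full scale, with an ordinal or rank-based method if ratings pile up at one end.
3. Keep the proportion of confident pupils as a descriptive summary only, at a cut fixed before data are seen.
4. Confirm that the 1.1.2 scale is in the pre/post questionnaire, worded so that untrained pupils and controls can answer it, and given to both arms at each test. If it is not there, add it.
5. If the sponsor does intend a two-category outcome, state the item or cut, give the reason, and amend 1.1.2 to match.

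The cost is a wording change and, if the scale is missing, a few extra questionnaire items. No added pupils or visits are needed. A difference in mean rating is less direct for teachers than a percentage, which the descriptive proportion covers. Baseline ratings cannot be recovered once pre-testing is done without the scale; in that case only a post-test comparison would remain.
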